1.4.4 Immunogenicity of Urelumab

Data from previous studies indicate that the overall rates of immunogenicity in patients treated with urelumab range from 11% (CA186001) to 27% (CA186006).

1.5 Overall Risk/Benefit Assessment

Subjects who have advanced solid tumors or B-cell NHL have extremely poor prognosis with limited curative options as stated in [Section 1](#).^{29,31} Nivolumab has demonstrated clinical activity in subjects with advanced NSCLC, RCC, MEL and lymphomas among other tumors.

Nivolumab monotherapy has demonstrated clinical activity across several tumor types, including advanced, previously treated melanoma. The combination of nivolumab and urelumab has the potential for increased benefit compared to nivolumab monotherapy.

Nivolumab has also demonstrated a manageable safety profile. The most common AEs included fatigue, rash, pruritus, diarrhea, and nausea. Side effects of nivolumab therapy may include those associated with immune mediated activation, such as thyroiditis and transaminitis. In addition, < 1% subjects who developed pneumonitis have died. To mitigate risk to subjects management algorithms for nivolumab-related adverse events from prior collective nivolumab experience have been included ([Appendix 3](#)).

Pharmacodynamic evidence of biologic activity was noted with urelumab monotherapy doses ranging from 0.1 mg/kg to 10 mg/kg. Clinical anti-tumor activity was also noted in subjects treated at urelumab doses starting at a 0.1 mg/kg dose in the Phase 1 monotherapy studies. Among solid tumors, anti-tumor activity was manifested in both objective responses and stable disease. All objective responses were observed in subjects with melanoma, and subjects with RCC and ovarian cancer were noted to have stable disease.

In study CA186006, one subject with metastatic melanoma developed a complete response and 7 of 41 showed stable disease. The complete response seen at 0.1 mg/kg and similar stable disease rates at 0.1 mg/kg and 1.0 mg/kg in study CA186006 suggest that there is anti-tumor activity at the initial dose level of 0.1 mg/kg. The similar stable disease rates of 1.0 mg/kg q3w and 1.0 mg/kg

q6w in study CA186006 suggest that a less frequent dosing interval may not impact efficacy, but may improve the safety profile. Pharmacodynamic evidence of biologic activity was also observed across the same dose range. In hematologic malignancies, objective responses were observed in 10 subjects with B-cell NHL treated at 0.3 mg/kg, including one complete response based on preliminary data from CA186011 (Part 3 of cohort expansion).

Taken together, these data provide evidence for further evaluation of the potential benefit of urelumab in combination nivolumab in solid tumors and B-cell NHL (in particular patients with the DLBCL or FL subtypes of B-cell NHL).

Hepatotoxicity is the most frequent clinically significant drug-related AE experienced among subjects treated with urelumab and is dose and potentially schedule dependent. However, the risk of hepatotoxicity at doses being tested in the current study (flat dose of 8 mg) is expected to be very low ([Sections 1.1.1](#) and [1.4.3](#)). In a prior monotherapy study (CA186006), that evaluated a dose of 0.1 mg/kg of urelumab which correlates with 8 mg flat dose, only 1 event of drug-related \geq Grade 3 AST elevation was noted in the 41 subjects treated at the 0.1 mg/kg dose, and no other Grade \geq 3 hepatic events occurred at this dose. In addition, in the ongoing monotherapy study CA186011 (Part 4 initiated in May 2014) exploring the 0.1 mg/kg dose of urelumab, no hepatic DLTs were observed during the dose escalation period with this dose, and no \geq Grade 3 hepatic events were noted in subjects subsequently dosed at 0.1 mg/kg urelumab (preliminary safety data).

The possibility exists that the combination of urelumab and nivolumab will be more hepatotoxic than urelumab monotherapy, but this is considered unlikely since nivolumab monotherapy has not been associated with any significant hepatotoxicity. However, since this is an experimental study, the study protocol has been designed to minimize the risk of potential synergistic hepatotoxicity or unanticipated adverse events as follows:

1) **Enrollment Criteria** ([Section 3.3.1](#)) have been strictly chosen to minimize inclusion of subjects with underlying potential for increased hepatotoxicity from urelumab. Subjects with disease characteristics that could predispose to higher risk of morbidity during conduct of the study ie, patients with history of any hepatitis [eg, alcoholic or non-alcoholic steatohepatitis (NASH), drug-related, auto-immune] will be excluded from participation.

The safety monitoring plan will require weekly liver function tests (LFTs) including AST, ALT alkaline phosphatase, gamma-glutamyl transpeptidase (GGT), and total bilirubin during treatment with urelumab ([Table 5.1-1](#)), and weekly for the first 8 weeks following last treatment with urelumab ([Table 5.1-3](#)). As detailed in [Section 5.3.1](#) and Hepatotoxicity management algorithm ([Appendix 3](#)):

Management of LFT Elevations:

- Subjects experiencing \geq Grade 3 elevations in ALT, AST, or total bilirubin will be discontinued.
- Subjects experiencing ALT or AST $>$ 3x ULN with concurrent total bilirubin $>$ 2x ULN and fulfilling Hy's law criteria will be discontinued. If 2 events of Hy's Law (ALT or AST $>$ 3 X ULN and concurrent T Bili $>$ 2 X ULN) occurs at any

point in the study the entire cohort and all cohorts above will be considered to exceed the MTD and no subject will receive further doses at or above that dose level.

- Subjects experiencing Grade 2 elevations in ALT, AST or total bilirubin will have the next planned dose delayed until ALT, AST, and total bilirubin resolve to \leq Grade 1

2) **Hepatotoxicity management algorithm:** To mitigate risk to subjects who develop drug-related hepatotoxicity, specific guidelines and algorithm for management of hepatotoxicity (see [Appendix 3](#)), with links to online resources with a comprehensive listing of potentially hepatotoxic agents are included in this protocol.

Screening tests, and clinical and laboratory safety assessments will also be performed on an ongoing basis and monitored closely. In addition, the AEs and SAEs will be reviewed by the Medical Monitor/Study Director and the Pharmacovigilance group to look for trends and safety issues. It is possible that unforeseen, unknown, or unanticipated reactions may occur since urelumab is an investigational product.

In addition to the potential risk associated with administration of study drugs, there is also some risk associated with tumor biopsies, including bleeding, infection and pain. While there is no direct benefit to subjects who undergo these procedures, there is the distinct possibility that the data generated from these samples will guide the further development of these compounds and may be of direct benefit for others with advanced solid tumors.

Preliminary data in 138 patients treated with urelumab and nivolumab as of the clinical cutoff date of 30-Sep-2016, revealed that the most frequent TRAE was fatigue (31%); grade 3/4 ALT/AST elevations (2%/2%) and TRAEs leading to discontinuation (6%) were infrequent. No treatment-related deaths were reported. Twenty-five of 124 evaluable patients treated with the combination had objective responses (melanoma, n=23; SCCHN, n=1, NSCLC, n=1). The ORR in melanoma was 50% (23/46) including 9/18 of subjects with PD-L1 negative tumors by IHC.

There remains a significant unmet need for curative options in the tumor types being evaluated in this study including PD-L1 negative melanoma where the objective response rate to anti-PD-1 monotherapy is ~30-35%. Overall, the data indicate a favorable benefit/risk profile for the evaluation of a combination of urelumab with nivolumab in this study since the availability of more effective therapies or combination of agents would be of great benefit to these patients with advanced cancer.

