^b Nivolumab 3 mg/kg will be administered for subjects enrolled prior to Revised Protocol 02. Nivolumab 240 mg flat dose administered for subjects enrolled after Revised Protocol 02.

After dose escalation to the next cohort, 3-9 additional subjects may be enrolled in any previously tolerated (as defined by the dose escalation decision rules in [Table 3.1.5-2](#)) dose level (original 3-9 subjects from dose escalation plus additional subjects required to have a total cohort size of 12). If the rate of DLTs exceeds 33% in a given treatment regimen, the findings will be discussed and further enrollment may be interrupted for that specific treatment regimen and tumor type.

If one of the planned dose cohorts is determined to exceed the MTD, and/or based on ongoing safety/tolerability experience through the dose escalation phase of the study, an alternate dose escalation schema as outlined in [Table 3.1.5-3](#) may be explored in consultation and agreement between the Sponsor and investigators.

Sentinel Subject: During dose escalation, the first subject treated at each dose level will receive C1D1 (eg, the first dose of study drugs) and will be observed for 3 weeks such that one combination dose followed by one nivolumab dose are administered before additional subjects in the cohort receive the first dose of study drug (ie, C1D1).

Dose Escalation Rules: Table outlines the decision rules for dose escalation based on the number of subjects and observed DLTs. No intra-subject dose escalation or reduction is allowed. Subjects who withdraw from the study during the DLT period for reasons other than a DLT may be replaced within the same dose level/regimen. Dose escalation will be based on the number of dose limiting toxicities (DLTs) experienced during the DLT observation period.

If dose escalation is terminated, then the dose or dosing regimen below that which invoked the stopping rule will be declared the MTD.

Table 3.1.5-2: Decision Rules During Dose Escalation

Number of Evaluable Subjects/ Cohort	3-4 ^a			6-8			9-12	
Total Number of Observed DLTs	0	1	2 or more	1	2	3 or more	2	3 or more
Decision Rule	Dose Escalate	Enroll additional subjects in cohort to reach at least 6 subjects	Dose exceeds MTD	Dose Escalate	Enroll additional subjects at in cohort to reach at least 9 subjects	Dose exceeds MTD	Dose Escalate	Dose exceeds MTD

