3.1.6 Cohort Expansion

The purpose of cohort expansion is to gather additional safety, tolerability, preliminary efficacy and pharmacodynamic information regarding the combination of urelumab and nivolumab. Once the safety profile of all doses tested has been characterized and the MTD of combined administration of urelumab and nivolumab has been defined, cohort expansions will be initiated at the MTD, the HAD, or an alternate dose, if recommended by the investigators and the sponsor. Treatment doses in the cohort expansion groups will not exceed the HAD. The cohort expansion phase will follow a 2-stage design as outlined below in Table 3.1.6-1.

Table 3.1.6-1: Cohort Expansion

Tumor Types	Stage 1 Expansion	Stage 2 Expansion
Non-small Cell Lung Cancer (NSCLC)	Up to approximately 20 subjects at MTD or HAD	Up to approximately 20 additional subjects
Melanoma (MEL)	Up to approximately 20 subjects at MTD or HAD	Up to approximately 20 additional subjects
Head and Neck Squamous Cell Carcinoma (SCCHN)	Up to approximately 20 subjects at MTD or HAD	Up to approximately 20 additional subjects
Diffuse Large B Cell Lymphoma (DLBCL)	Up to approximately 20 subjects at MTD or HAD	Up to approximately 20 additional subjects
NSCLC (progressive or recurrent disease during or after anti-PD-1/anti-PD-L1 therapy)	Up to approximately 20 subjects at MTD or HAD	Up to approximately 20 subjects

Table 3.1.6-1: Cohort Expansion		
Tumor Types	Stage 1 Expansion	Stage 2 Expansion
Follicular Lymphoma (FL)	Up to approximately 20 subjects at MTD or HAD	Up to approximately 20 subjects
Melanoma (progressive or recurrent disease during or after an anti-PD-1/anti-PD-L1 containing treatment regimen)	Up to approximately 20 subjects at MTD or HAD	Up to approximately 20 subjects
Melanoma PD-L1 negative	Up to approximately 50 subjects at MTD or HAD	

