3.1.6.1 Stage 1 Cohort Expansion

Stage 1 of the expansion phase will treat 20 subjects per tumor type at the MTD or HAD as identified during dose escalation followed by continued enrollment of up to approximately 20 additional subjects (total of 40 subjects per tumor type) (Stage 2) to obtain additional safety/efficacy data for the combination. The safety, tolerability, and preliminary efficacy data from Stage 1 of the cohort expansion will be evaluated per tumor type and discussed by the sponsor with investigators prior to enrolling 20 additional patients during Stage 2.

Efficacy criteria for moving to Stage 2:

In order to enroll additional patients in Stage 2 of cohort expansion a minimum of 4 out of 20 subjects in the first stage of cohort expansion need to demonstrate an objective response to study therapy. In general, if 0 to 3 responses are observed in a given tumor specific cohort during Stage 1 of cohort expansion, Stage 2 will not be enrolled for that tumor type. Please note: Ongoing assessment of data from the initial 20 patients may be used to consider additional enrollment in that tumor type at a later date (to consider the possibility of delayed responses).

An additional 50 treatment naïve PD-L1 negative melanoma subjects will be treated at MTD/HAD to further evaluate if there is an efficacy signal in this population. Additional subjects may be enrolled and treated so as to accrue a minimum of 50 evaluable subjects with at least 2 on treatment scans.

Safety criteria for moving to Stage 2:

If the rate of events that would qualify as DLTs exceeds 33% for a particular tumor type; the findings will be discussed by sponsor with investigators and further enrollment may be interrupted for subjects with that tumor type.

Safety data from subjects enrolled in Stage 1 of the expansion phase will be reviewed by BMS medical and safety teams, and discussed with and endorsed by participating investigators, prior to moving to Stage 2 of cohort expansion.

If the efficacy and safety data from a given tumor type meet the minimum criteria for moving forward, approximately 20 additional subjects will be enrolled during Stage 2 of cohort expansion. The evaluation of data from Stage 1 and the decision to begin Stage 2 of the expansion phase of the study can be made up to one year following completion of the enrollment of Stage 1 for each individual tumor type.

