4.5.2 Dose Limiting Toxicities

Adverse events will be graded according to the National Cancer Institute (NCI) Common Terminology Criteria for Adverse Events (CTCAE) Version 4.0 (v4.0).

Non-hematologic Dose-Limiting Toxicity (DLT):

A. Hepatic Non-Hematologic DLT

Any one of the following study drug-related events will be considered a hepatic DLT:

- Any \geq grade 3 elevation of AST, ALT or T bili
- Grade 2 AST or ALT with symptomatic liver inflammation (eg, right upper quadrant tenderness, jaundice, pruritus)
- AST or ALT $> 3 \times$ ULN and concurrent total bilirubin $> 2 \times$ ULN without initial findings of cholestasis (elevated serum alkaline phosphatase (ALP) (ie, findings consistent with Hy's law or FDA definition of potential drug-induced liver injury or pDILI)*

*[Note that this special category of DLT uses ULN rather than CTC Grade for definition]

NOTE: Subjects who experience a DLT that is considered related only to urelumab may be allowed to continue nivolumab monotherapy following resolution of the event. This will be determined on a case by case basis, after specific consultation and agreement between the investigator and BMS Medical Monitor in settings where benefit/risk may justify continued treatment with nivolumab

monotherapy (eg, subjects with asymptomatic, isolated grade 3 ALT and/or AST elevation that responds rapidly to short 2-3 weeks course of steroid therapy).

B. Non-Hepatic Non-Hematologic DLT

Any of the following events will be considered a Non-Hepatic Non-Hematologic DLT:

- Any Grade 2 drug-related uveitis or eye pain or blurred vision that does not respond to topical therapy and does not improve to Grade 1 severity within 2 weeks OR requires systemic treatment
- Grade 3 drug-related uveitis, pneumonitis, bronchospasm, neurologic toxicity, hypersensitivity reaction, or infusion reaction of any duration requires discontinuation
- Any Grade 3 or greater non-dermatologic, non-hepatic non-hematologic study drug-related toxicity will be considered a dose-limiting toxicity with the following specific EXCEPTIONS:
 - Grade 3 or grade 4 electrolyte abnormalities that are not complicated by associated clinical adverse experiences, last less than 48 hours and either resolve spontaneously or respond to conventional medical intervention
 - Grade 3 nausea, vomiting or diarrhea that lasts less than 48 hours, and either resolves spontaneously or responds to conventional medical intervention

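### The two-event Hy's Law stop in Section 1.5 conflicts with the escalation table at 6-12 evaluable subjects, is not carried into the expansion safety criterion, and is given no stated precedence

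*Protocol*

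**What the plan says.** - **The stop.** Protocol Section 1.5 (Management of LFT Elevations) takes ALT or AST above 3 times ULN with concurrent total bilirubin above 2 times ULN. Two such events at any "point in the study the entire cohort and all cohorts above will be considered to exceed the MTD and no subject will receive" more treatment at that level or higher. The section refers to 5.3.1 and Appendix 3 for detail. Section 5.3.1 gives the liver-test schedule and points to Appendix 3; it does not repeat the rule.
- **How one event counts.** Section 4.5.2 introduces its list with "Any one of the following study drug-related events will be considered a hepatic DLT". The drug-related Hy's Law pattern is on that list beside Grade 3 enzyme elevations, with no extra weight.
- **Escalation.** Section 3.1.5 says "Dose escalation will be based on the number of dose limiting toxicities (DLTs) experienced during the DLT observation period", a period of 8 weeks. For two DLTs in 6-8 evaluable subjects Table 3.1.5-2 reads "Enroll additional subjects at in cohort to reach at least 9 subjects"; in 9-12 it says to escalate; in 3-4 it says the dose is above the MTD. Synopsis Table 2 and SAP Table 3 give the same decisions.
- **Expansion.** Under 3.1.6, "Treatment doses in the cohort expansion groups will not exceed the HAD". In 3.1.6.1, when DLT-type events exceed 33% in a tumor type, "the findings will be discussed by sponsor with investigators and further enrollment may be interrupted for subjects with that tumor type". The same section adds 50 treatment-naive PD-L1 negative "melanoma subjects will be treated at MTD/HAD to further evaluate if there is an efficacy signal in this population".
- **Stage of the trial.** Section 1.5 reports "Preliminary data in 138 patients treated with urelumab and nivolumab as of the clinical cutoff date of 30-Sep-2016", and 3.1.6 starts expansion only once the MTD is defined.

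**The concern.** Identifying the MTD is part of the primary objective (1.3.1). One section turns two Hy's Law events into a mandatory dose-level stop. The table that decides escalation can turn the same two events into an instruction to continue.

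The liver risk is documented. Section 1.4.3 reports two fatal hepatotoxicity cases on urelumab monotherapy. It also reports that a single potential drug-induced liver injury at 0.3 mg/kg in CA186011 led to that dose being judged above the MTD under that protocol's guidance.

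Section 7 provides no data monitoring committee, so the sponsor and investigators apply the written rules themselves. The stop is stated in a background section, while escalation and Stage 2 decisions are described in 3.1.5 and 3.1.6.1. At stake is whether other subjects at the dose level stop treatment when the second event occurs.

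**Working it through.** The plan states no figure for this point that could be reproduced, so the check sets the rules side by side and then does simple arithmetic on the 33% criterion.

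**1. Two events during escalation.** Inputs: Section 1.5, Section 4.5.2, Table 3.1.5-2.

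| Evaluable subjects | Table 3.1.5-2 at two DLTs | Section 1.5 at two Hy's Law events | Agree? |
|---|---|---|---|
| 3-4 | Above MTD | Above MTD, dosing ends | Yes |
| 6-8 | Enroll to at least 9 | Above MTD, dosing ends | No |
| 9-12 | Escalate | Above MTD, dosing ends | No |

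One cell agrees and two do not. The clash has conditions:
- both events are drug-related and lack initial cholestasis (4.5.2);
- both fall within 8 weeks;
- there is no third DLT, since three or more in 6-12 subjects is above the MTD under the table as well.

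Events after week 8 fall outside the table, and only Section 1.5 covers them.

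The meaning of the escalate cell depends on the dose. At 3 mg every 4 weeks it sends the trial to 8 mg, which Section 1.5 would also close because it covers higher cohorts. At 8 mg, the highest planned dose, it amounts to clearing the dose.

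**2. Two events during expansion.** Inputs: cohorts of 20 (Stage 1), 40 (both stages) and 50 (PD-L1 negative melanoma), and the criterion of a rate above 33%. The last cohort has no Stage 2, so 50 is the denominator only if the criterion is applied to that cohort alone. The smallest count k with k/n > 0.33 is:

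- n = 20: 6/20 = 30%, 7/20 = 35%, so k = 7. Two events are 2/20 = 10%.
- n = 40: 13/40 = 32.5%, 14/40 = 35%, so k = 14. Two events are 2/40 = 5%.
- n = 50: 16/50 = 32%, 17/50 = 34%, so k = 17. Two events are 2/50 = 4%.

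The criterion therefore needs 7/2 = 3.5, 14/2 = 7 or 17/2 = 8.5 times as many events as the Section 1.5 stop. If the two events fall in two Stage 1 cohorts, each shows 1/20 = 5%. The consequences differ too: Section 1.5 ends dosing at the level, while 3.1.6.1 leads to discussion and possibly a pause in enrollment for that tumor type.

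**3. Is precedence stated anywhere?** Neither the stop nor a statement of which rule governs appears in Sections 3.1.5, 3.1.6, 4.5.2, 4.5.5, 4.5.7, 5.3.1, 6.6 or 6.7.2, or in SAP 2.1.1 and 2.1.2.1. Appendix 3 was not in the text available, so its content is unknown.

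**The case against.** The best reply is that an additional stop is not a contradiction. Section 1.5 is unconditional, and nothing in 3.1.5 or 3.1.6.1 permits dosing once another protocol stop has been met. A dose can be required to pass both rules, and 3.1.5 itself lets ongoing safety experience redirect escalation. This is a reasonable reading and probably the intended one. But 3.1.5 also bases escalation on the DLT count, and two of its cells give the opposite instruction with no cross-reference.

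Second, the direct clash lies in a phase that appears finished, and in expansion the stop is merely not repeated. Both points stand and limit the size of the finding.

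Third, the sponsor would hear of each case promptly. Section 6.7.2 requires expedited notification of potential Hy's Law cases, and 6.6 with 6.1.1 makes potential liver injury reportable as an SAE within 24 hours. There is also safety review before Stage 2 and a cross-tumor review for unforeseen toxicity. These are real safeguards, but none states what happens to the dose level at the second event.

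Fourth, the trigger is not settled. Section 4.5.2 excludes cholestasis and 6.7.2 excludes alternate causes. The parenthesis in Section 1.5 does neither, although its preceding sentence refers to Hy's Law criteria. Section 1.5 also does not say whether cohort means a dose level or a tumor-specific group. Both matters are for the sponsor, so a fix should not decide them silently.

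**Conclusion.** The point holds and is modest in size. For two in-window, drug-related Hy's Law events with no other DLT, Section 1.5 and the escalation table agree at 3-4 evaluable subjects and disagree at 6-8 and 9-12. The expansion criterion is silent on the stop, and two events fall far below its trigger (10%, 5% or 4% against more than 33%).

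Three stronger readings are tempting and not supported:
- A reader might infer that the protocol allows dosing to continue after two events. It does not: Section 1.5 forbids it, and the defect is that the operative sections do not say that this governs.
- A reader might infer that 3.1.6.1 contradicts Section 1.5. It only omits the stop.
- A reader might try to size the defect by the chance of two events in a cohort. The documents give no Hy's Law rate, and such a figure would show how often the stop fires, not how often it would be missed.

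The conclusion rests on two assumptions: that Appendix 3 contains no precedence statement, and that escalation is complete. The second is inferred from the 138 treated patients and the order of phases, and it makes expansion the main present relevance.

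**What to change.** Add one sentence to 3.1.5, as a footnote to Table 3.1.5-2 and synopsis Table 2, and one to the safety criteria in 3.1.6.1. For example: *The two-event Hy's Law stop in Section 1.5 applies at any time in the study, is counted by dose level, and overrides the DLT-count decision rules and the 33% criterion.*

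The sponsor should confirm the dose-level reading of cohort before adopting it, since it would count events from all tumor types treated at that dose. The trigger stays as Section 1.5 words it, with no exclusions added. Mirroring the sentence in SAP 2.1.1 and 2.1.2.1 is optional, because SAP 2.1 gives only the main design points and refers to the protocol.

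The cost is amendment wording in two protocol sections and the synopsis, plus one sponsor decision on how events are pooled. No new data, visits or subjects are needed.
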